9.3 Institutional Review Board/Ethics Committee

This protocol and/or other relevant study documents must be submitted to the appropriate local or central IRB/EC. Written approval must be obtained before commencement of the study.

Approval obtained from the IRB/EC should document the version of the protocol and consent that is being approved. All amendments to the protocol will also be submitted to the same IRB/EC.

9.4 Data Protection

All information collected during the course of this study will be kept strictly confidential. Any information that could identify a subject will remain with the investigator where it will be archived with study documents. Subjects will remain anonymous for the purposes of data analysis. Data collected for the purposes of this study should be made available for Coloplast or designated contracted monitors at all monitoring visits. A contracted statistician will conduct data analysis and provide data tables to the sponsor.

9.5 Risks and Benefits

Subjects participating in the study will be exposed to the same operative and post-operative risks as patients undergoing surgical procedures for single-incision or traditional full length sling devices not associated with study participation. Risks can be minimized through the use of strict aseptic technique, compliance with this protocol and technical implant procedures, adherence to the guidelines for subject selection, close monitoring of the subject during implant and follow-up, and by promptly supplying the sponsor with all pertinent information in a timely manner. Risks to study subjects will be further minimized by providing appropriate training to study investigators new to using Coloplast products and by study monitoring during the course of this clinical study.

As with any surgical treatment for incontinence, there is always the risk that the treatment will not be successful or that incontinence will recur. There is a risk that, if the mesh causes problems, (e.g. extrusion - defined as mesh exposure in the vagina, pain, or infection), removal of the mesh may be necessary, and complete removal of the mesh may not be possible. Problems may persist, with or without complete mesh removal. These residual risks will be mitigated by pre-implant patient education, informed consent, selection of experienced surgeons for participation in the study, appropriate patient selection, appropriate device-implant training for physicians new to using Coloplast slings, and use of good medical and surgical technique to avoid known and potential causes of mesh problems.

Anticipated risks of use of the study device are listed in Section 14. Potential risks of participation in the study include, but are not limited to:

- Inadvertent sharing of study subject information that is intended to be private

Potential benefits of the study device include, but are not limited to:

- Cure or improvement of stress urinary incontinence
- Improvement of quality of life

10 Data Management

Data will be captured in a database using eCRFs to accommodate specific features of the study design and will be used to capture study specific data. Training will be provided for all study personnel entering data into the database prior to being given access to the database.

Edit checks will be created for quality control. Data will be subject to initial inspection for omitted data, data inconsistencies, and deviations. The resolution of any inconsistencies will be resolved through data queries. The site will be asked to review and respond to the data queries.

Study staff delegated by the principal investigator may complete the eCRF; however, the principal investigator will review all eCRFs for completeness and will electronically sign the forms.

11 Amendments to the Clinical Study Plan

Changes to the Clinical Study Plan are not permitted without Sponsor approval. Any significant changes to the study plan must be:

- Agreed to by the Principal Investigator
- Registered in the Change Log.
- Approved by the IRB/EC prior to implementation (if applicable).
- Approved by the appropriate regulatory authorities prior to implementation (if applicable).

12 Clinical Study Deviations

A clinical study deviation is defined as an event where the clinical investigator or site personnel did not conduct the study in accordance to the Clinical Study Plan or the investigator agreement. No deviations are allowed from the study protocol unless under emergency circumstances and to protect the rights, safety and well-being of the subject(s). All deviations must be documented. Deviations must be reported to the sponsor and to the local IRB/EC per the specific reporting requirements. In the case of continued or repeated deviations affecting subject rights, safety and well-being, the sponsor may terminate the PI from further participation in the study.

13 Statement of Compliance

The clinical study is conducted, (as applicable to the geographic region of each individual clinical site) in accordance with:

- CFR Title 21: Part 11 – Electronic Records; Electronic Signatures
- CFR Title 21: Part 50 – Protection of Human Subjects
- CFR Title 21: Part 54 – Financial Disclosures by Clinical Investigators
- CFR Title 21: Part 56 – Institutional Review Boards
- ISO 14155:2011 (E) (as regionally applicable)
- Ethical principles that have their origin in the Declaration of Helsinki, 1964, Last amended at the 59th WMA General Assembly, Seoul, October 2008.
- ICH Guidelines for Good Clinical Practice (E6 or E6 R1, as regionally applicable)
- Guidance for Industry Investigator Responsibilities – Protecting the Rights, Safety, and Welfare of Study Subjects, October 2009
- Guidance for Clinical Investigators, Sponsors, and IRBs Adverse Event Reporting to IRBs – Improving Human Subject Protection, January 2009

14 Adverse Events, Serious Adverse Events, and Device Deficiencies

14.1 Adverse Event/Complication Classification

Collection of Adverse Events will begin at the time the first incision is made for the index surgical procedure and will continue until the subject's study participation is complete. The investigator will be asked to assess the relationship of the event to the implanted study product, the implant study procedure, and the presence or performance of the mesh itself for each adverse event reported. Serious and non-serious adverse events will be collected and reported for this study.

The principal investigator will ensure that adequate medical care is provided to all subjects experiencing an adverse event during or after participation in the clinical investigation. Any ongoing adverse events must be assessed on an ongoing basis to determine resolution.

The current status of all ongoing adverse events is documented at the time of site close-out. The resolution date will be recorded on an adverse event eCRF.

14.1.1 Adverse Events (AE)

An adverse event (AE) is any untoward medical occurrence, unintended disease or injury, or untoward clinical sign (including abnormal laboratory findings) that may occur in subjects, users or other parties, whether or not it is related to the medical device(s), or the procedure's involved. Potential adverse events include but are not limited to:

- Erosion - Defined as movement of mesh into any other organ or body plane.
- Exposure – Defined as a condition of displaying, revealing, exhibiting or making accessible (e.g. vaginal mesh visualized through separated vaginal epithelium)
- Extrusion - Defined as passage gradually out of a body structure or tissue.
- Sling Migration - Defined as movement from the original implanted mid-urethral site.
- Transient or permanent urinary retention/obstruction.
- Foreign body reaction - Defined as absence of tissue in-growth resulting in the presence of granulation tissue.
- Reaction from anesthesia (respiratory failure, allergic reaction, thromboembolic event)
- Vaginal discharge
- Abscess
- Pain
- Delayed wound healing
- De novo or worsening urgency/overactive bladder
- De novo or worsening dyspareunia
- Genital/pelvic pain
- Hematoma and/or hemorrhage
- Infection
- Inflammation
- Paresthesia (genital)
- Scar tissue formation
- Bladder perforation
- Urethral perforation
- Bowel perforation
- Voiding dysfunction
- Worsening incontinence

- Urethral obstruction
- Vascular injury
- Nerve injury
- Urinary tract infection

14.1.2 Serious Adverse Events

A serious adverse event (SAE) is an adverse event that led to:

- Life Threatening: The participant was at imminent risk of dying at the time of the adverse event.
- Permanent Impairment: An adverse event that resulted in permanent impairment of a body function or permanent damage to a body structure.
- Necessitates Intervention: An adverse event that resulted in a condition that necessitates medical or surgical intervention to preclude permanent impairment of a body function or damage to a body structure.
- Hospitalization/Prolongs Hospitalization: Requires inpatient hospitalization or prolongs an existing hospitalization. Planned hospitalization for a pre-existing condition is not considered a serious adverse event.
- NOTE: Emergency room visits that do not result in admission to the hospital should be evaluated for one of the other serious outcomes (e.g., life-threatening; required intervention to prevent permanent impairment or damage; other serious medically important event).
- Results in Death: An adverse event that results in the participant's death.

14.1.3 Unanticipated Adverse Device Effect (UADE)

Any serious adverse effect on health or safety or any life-threatening problem or death caused by, or associated with, a device, if that effect, problem, or death was not previously identified in nature, severity, or degree of incidence in the study plan or application (including a supplementary plan or application), or any other unanticipated serious problem associated with a device that relates to the rights, safety, or welfare of subjects.

14.1.4 Adverse Event Severity Classification and Device Causality

The investigator will classify adverse events by relatedness to the device or procedure, as follows:

A **device related** adverse event is an event that results from the presence or performance of the device. In this study, the device is the Altis Sling or control device (transobturator or retropubic sling). Device related events can include, but are not limited to: erosion, extrusion, urinary retention, sling migration and foreign body reaction.

A **procedure related** adverse event is an adverse event that occurs due to the implant procedure.

The investigator will classify adverse events by severity, as follows:

A **Mild** event is an adverse event that is reported without any action(s) taken.

A **Moderate** event is an adverse event that is not severe, but requires action.

A **Severe** event is an adverse event that results in a subject's hospitalization, or their hospitalization is unduly prolonged because of potential disability or danger to life, or an intervention has been necessitated, or the event is terminal.

14.2 Device Deficiency and Technical Observations

A device deficiency refers to the inadequacy of the medical device with respect to its identity, quality, durability, reliability, safety or performance. This includes malfunctions, misuse or user errors and inadequate labeling.

A technical observation is a failure or malfunction of the device, or a device/system functioning not according to the design intent that does not result in subject symptoms.

Examples of device deficiencies and/or technical observations include, but are not limited to: mechanical failure of the mesh, mesh does not withstand insertion or in use of forces when inserted, defect in mesh when removed from package.

15 Adverse Event Review

15.1 Clinical Events Committee

A clinical events committee (CEC) will be used to adjudicate device and procedure related serious adverse events. Additional adverse events may be specified for CEC adjudication throughout the study. The CEC adjudication of adverse events will be used for data analysis. The CEC will be made up of a group of independent physicians specializing in the treatment of SUI. Responsibilities of the CEC may include, but are not limited to reviewing individual adverse events to determine severity and relationship to the study device and/or procedure.

16 Reporting and Timelines

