5.6 Blinding

Study subjects and investigational study personnel are not blinded to study group assignment.

6 Identification and Description of Devices

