12.7.5. All Adverse Events

All adverse events will be summarized through 6, 12, 18, 24, and 36 months. The proportions of subjects with events will be reported as well as Kaplan-Meier event rates at the time points of interest. No imputation for missing data for the rates of adverse events is planned (with the exception of the secondary safety endpoints noted above). All safety summarized are based on mITT analysis population. Adverse events for subjects excluded from mITT analysis population (i.e., enrolled, but no implant was attempted) will be listed separately.

For subjects with revision or resurgery within 36 months of the index surgery, the rates of adverse events peri-procedural (within 30 days) following revision or resurgery will be assessed. Peri-operative adverse events will be summarized by relatedness separately for each treatment group.

Clinical Events Committee (CEC) will be used to adjudicate device and procedure related serious adverse events, and other events as deemed appropriate. The CEC adjudication will be used for all safety analyses. If an adverse event has not been reviewed by the CEC, the investigator's assessment will be used for all safety analyses.

Both the CEC and the investigator will assess the device and the procedure relatedness of the adverse event. The relatedness will be categorized as "definite", "probable", "possible", "not related" or "unknown". If the event is categorized as having a "definite", "probable" or "possible" relationship, it will be considered related for all safety analyses.

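### Events-committee review is guaranteed only for SAEs counted as device- or procedure-related, so an SAE called unrelated or unknown can leave the primary safety endpoint without independent review

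*Protocol*

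**What the plan says.** - **Endpoint.** Protocol 3.3.1 and SAP 12.5.1 define primary safety as device- and/or procedure-related SAEs through 36 months.
- **First relatedness call.** Protocol 14.1.4 gives it to the investigator. Protocol 5.6 states: "Study subjects and investigational study personnel are not blinded to study group assignment". There is no randomisation (Protocol 5.5).
- **Committed committee scope.** Protocol 15.1: "A clinical events committee (CEC) will be used to adjudicate device and procedure related serious adverse events". SAP 12.7.5 has the clinical events committee (CEC) "adjudicate device and procedure related serious adverse events, and other events as deemed appropriate".
- **Optional scope.** Protocol 15.1 adds: "Additional adverse events may be specified for CEC adjudication throughout the study". Possible committee tasks include "reviewing individual adverse events to determine severity and relationship to the study device and/or procedure".
- **Which call is analysed.** Protocol 15.1: "The CEC adjudication of adverse events will be used for data analysis". SAP 12.7.5 adds a fallback: for an event the CEC has not reviewed, the investigator's "assessment will be used for all safety analyses".
- **What counts as related.** SAP 12.7.5 counts definite, probable and possible. Not related and unknown are the two categories outside that set.

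**The concern.** Relatedness is part of the endpoint definition, so whoever makes the final relatedness call determines the numerator. An SAE classed as related has a committed independent check. An SAE classed as not related or unknown has none: it may be referred, but nothing says who refers, when, or on what criterion. If it is not referred, the fallback keeps the call of someone who knows which sling was implanted.

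The guaranteed review is therefore asymmetric. It protects against SAEs wrongly counted, but not against SAEs wrongly left out. In a non-inferiority test of an absolute difference against a fixed margin, leaving out true events can shrink the observed difference and make the test easier to pass. What is at stake is the credibility of one of the two objectives that must both be met for study success.

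**Working it through.** **1. Route of an SAE through the plan**

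| Investigator's call | Is CEC review committed? | Call used if there is no CEC review |
|---|---|---|
| Definite, probable or possible | Yes, if the investigator's call defines the set | Investigator: counts |
| Not related | No; discretionary referral | Investigator: does not count |
| Unknown | No; discretionary referral | Investigator: outside the related set |

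If instead the CEC itself decides which SAEs are related, it would have to see every SAE. Neither document says that it does, and the SAP fallback expressly provides for events it has not reviewed. Under either reading, review of the last two rows is not guaranteed.

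**2. The plan's own safety figure**

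Inputs from Protocol 7.9.3 and 7.9.5: 10% in each group, margin 0.10, 80% power, one-sided 0.025.

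n per group = (1.96 + 0.8416)² × (0.10×0.90 + 0.10×0.90) / 0.10² = 141.3, rounded up to 142. This is the SAP 10.2 figure. Dividing by (1 − 0.20) gives 177.5, rounded up to 178, the Protocol 7.9.3 figure. Both reproduce. Nothing in this point changes the sample size.

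**3. Illustration of the effect on error**

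Assumptions that are not in the documents: true rates at the null boundary (Comparator 0.10, Altis 0.20), and a fraction u of truly related SAEs called unrelated or unknown and never reviewed, with u set at 10% or 20%. For simplicity, u is applied to the proportion of women with an event. The denominator is 178 per arm, because the SAP keeps women with missing 36-month data in the analysis as event-free.

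With observed rates c (Comparator) and t (Altis), and d = t − c:

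SE = √{[c(1−c) + t(1−t)] / 178}

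Chance of falsely declaring non-inferiority = Φ[(0.10 − d)/SE − 1.96]

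At u = 0, d = 0.10 and the error is Φ(−1.96) = 2.5%.

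| Where the loss occurs | u | c | t | d | SE | Error |
|---|---|---|---|---|---|---|
| Altis only | 10% | 0.10 | 0.18 | 0.08 | 0.0365 | Φ(−1.413) = 7.9% |
| Altis only | 20% | 0.10 | 0.16 | 0.06 | 0.0355 | Φ(−0.833) = 20.2% |
| Both arms equally | 10% | 0.09 | 0.18 | 0.09 | 0.0359 | Φ(−1.681) = 4.6% |
| Both arms equally | 20% | 0.08 | 0.16 | 0.08 | 0.0342 | Φ(−1.375) = 8.5% |
| Comparator only | 10% | 0.09 | 0.20 | 0.11 | 0.0369 | Φ(−2.231) = 1.3% |
| Comparator only | 20% | 0.08 | 0.20 | 0.12 | 0.0362 | Φ(−2.512) = 0.6% |

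Exact binomial enumeration of the planned confidence-interval rule shows the same pattern. The error is 2.7% with no loss; for u = 10% and 20% it is 8.4% and 21.0% (Altis only), 5.0% and 9.2% (both arms), and 1.4% and 0.7% (Comparator only).

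**The case against.** A reader might infer that the committee sees only SAEs already called related, and so can remove events from the endpoint but never add one. The documents do not support that. Both allow other events to be referred, the committee's tasks may include determining relationship, and SAP 12.7.5 has both the committee and the investigator assess relatedness. A referred SAE can be upgraded. Nor does either document say that an SAE called unrelated is withheld from the committee.

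A reader might also infer that the bias favours Altis. Nothing in the documents shows that investigators under-call Altis events. The sponsor's commercial interest is a weak argument, because it also makes the control slings named in Protocol 6.2, although other FDA-cleared slings may be used.

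There are safeguards:

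- Every SAE, whatever its relatedness, must reach the sponsor within 24 hours or the next business day (Protocol 16.1, Table 3), so any SAE can be referred.
- The committee is independent: "The CEC will be made up of a group of independent physicians specializing in the treatment of SUI".
- Possible counts as related, which makes the related class broad.
- Revision/resurgery is tested with the same 0.10 margin and needs no relatedness call. All adverse events are also summarised by group.
- A committee charter outside these documents may set a referral rule.

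These points limit the concern but do not remove it. Permission to refer is not a rule, and the other analyses do not correct the primary endpoint. A charter could close the gap in practice, but the SAP fallback would still stand, and neither document commits the committee to all SAEs or states that it is masked to device.

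**Conclusion.** The point holds as a gap in what the plan guarantees. Independent review is assured only for device- or procedure-related SAEs, the documents do not say whose call defines that set, and an unreviewed SAE keeps an unblinded call.

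The size and direction of any resulting bias cannot be determined from the documents. The illustrated error runs from 0.6% to 20.2% against a nominal 2.5%, depending on where the loss falls. It rests on assumed miss rates and on true rates placed exactly at the margin, so it is not a prediction. Bias between arms is not needed for harm: equal under-calling in both arms also raises the error, while loss in the Comparator only makes the test conservative. The endpoint remains analysable. The change should be made, because the weakness affects a primary endpoint and can be avoided.

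**What to change.** Amend Protocol 15.1 and SAP 12.7.5 so that the existing CEC adjudicates the relatedness of every SAE, whatever category the investigator assigned, from files masked to device where feasible, and so that the CEC decision is used for the primary safety endpoint. The investigator fallback would then no longer apply to SAEs; it could remain for non-serious events.

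The change needs no new committee, visits or subjects and leaves the sample size as it is. SAEs are already reported to the sponsor, and Protocol 16.1 already lets the sponsor request de-identified source records. The downside is extra work for sites, sponsor and committee to retrieve, mask and review the SAE files that would not otherwise have gone to the CEC, in a study of 356 women. Masking may be incomplete where operative records reveal the type of sling.

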16.1 Investigator Reporting Responsibilities

In addition to the requirements stated in the investigator agreement, the investigator is responsible for the preparation (review and signature) and retention of the records cited below. All of the records below, with the exception of case history records, should be kept in the Investigator Site File (i.e., study binder). The following records are subject to inspection and must be retained according to the agreed upon timeframe in the investigator agreement (or longer, if local law or hospital administration requires) after study closure.

- All substantial correspondence that pertains to the conduct of the study. Any correspondence describing rationale for decisions made affecting subject safety and privacy or data collection and reporting is considered substantial correspondence
- Subject's case history records including: signed informed consent/applicable privacy protection authorization form; observations of adverse events/adverse device effects; medical history; implant and follow-up data; documentation of the dates and rationale for any deviation from the protocol
- Signed Investigator Agreement and current curriculum vitae (CV)
- Ethics committee documentation
- Site personnel training records

The investigator is responsible for the preparation (review and signature) and submission to the sponsor of all eCRFs, adverse events (reported per the country-specific collection requirements), deaths, and any deviations from the study plan. These reports are also subject to inspection and to the retention requirements described above for investigator records. If any action is taken by an IRB/EC with respect to the clinical study, the information must be forwarded to the Sponsor.

Table 3 Investigator Reporting Requirements

Report	Submit To	Description/ Constraints
AE – Adverse Event	Sponsor, IRB/EC (per local requirements)	Any adverse event must be reported as soon as possible via the EDC system
SADE - Serious Adverse Device Effect	Sponsor, IRB/EC (per local requirements)	Any adverse device effect must be no later than 24 hours or the next business day after first learning of the event
SAE-Serious Adverse Event	Sponsor, IRB/EC (per local requirements)	Any serious adverse event must be reported no later than 24 hours or the next business day after first learning of the event
UADE-Unanticipated Adverse Device Effect	Sponsor, IRB/EC	If an unforeseen complication is determined to be a Serious, device related, unanticipated AE then the investigator's report must be submitted as soon as possible but no later than within 24 hours or the next business day after the investigator first learns of the event
Withdrawal of IRB/EC approval	Sponsor	Notification within 24 hours or next business day
Progress Report (US only)	Sponsor IRBs	The investigator must submit this report annually, unless IRB requires more frequent submissions
Deviation from study Plan	Sponsor IRBs/ECs	Any deviation from the study plan must be reported to the Sponsor via the EDC system and reviewing local IRB/EC per local reporting requirements
Failure to obtain informed consent	Sponsor IRBs/ECs	In the US, the investigator must submit notification within 5 working days after device use.
Final report (US only)	Sponsor IRBs	This report must be submitted within 3 months of study completion or termination.
Device deficiency or technical observation	Sponsor, IRB/ECs per local reporting requirements	Notification within 24 hours or the next business day.

All adverse events listed above must be reported using the relevant adverse event/serious adverse event/device deficiency eCRF in the EDC system.

Source documentation for adverse events, including medical history, operative data, follow-up visit notes, any hospitalization records may be requested by Coloplast. If requested, please submit redacted/de-identified source documentation with the subject ID to:

Name: Coloplast Clinical Department

Address: [name]

City, State: Minneapolis, MN 55406

[contact]

[contact]

Email: [contact]

Table 4 Coloplast Reporting Requirements

Report	Submit To	Description
UADE-Unanticipated Adverse Device Effect	Investigators IRBs/ECs as applicable, FDA	Notification within 10 working days after the sponsor first learns of the effect.
Withdrawal of IRB/local ethics committee approval	Investigators IRBs/ECs, as applicable FDA	In the US, Notification within 5 working days.
Recall and device disposition	Investigators IRBs ECs, as applicable FDA	Notification within 30 working days and will include the reasons for any request that an investigator return, repair, or otherwise dispose of any devices.
Progress Reports (If required by local law)	Investigators IRBs/ECs, as applicable FDA	Every 6 months for the first 2 years, then annually after.
Final report	Investigators IRBs/ECs, as applicable FDA	Coloplast will notify the investigators of the completion or termination of the study. A final report will be submitted to the investigators and IRBs/MECs within three months after completion or termination of this study. In Europe, the investigator must confirm the receipt of the final report composed by Coloplast (and confirm agreement with the study results)

